Options for refractory HS include an alternate antibiotic regimen of clindamycin and rifampin or dapsone, and oral tretinoin. Response to antibiotic therapy is usually seen within 10 to 12 weeks of therapy. Efficacy of the clindamycin and rifampin regimen is extrapolated from uncontrolled studies and traditionally this combination therapy has not been provided long-term due to concern for adverse effects, although some have challenged this (25, 26, 27, 28). Dapsone may have some effect for mild to moderate HS, based on a small uncontrolled study, but requires laboratory monitoring for hematologic toxicity (29).

Adalimumab is the only approved therapy for the treatment of moderate to severe HS based on the results of two Phase 3, randomized, controlled trials, PIONEER I and PIONEER II. In PIONEER I, 42% of treated patients achieved HiSCR50 versus 26% of placebo-treated patients at Week 12. In PIONEER II, 59% of treated patients achieved HiSCR50 versus 28% of patients who received placebo. Despite notable clinical effect of systemic biologic therapy in large-scale placebo-controlled trials, it should be noted that 41% to 58% of patients did not achieve clinical response (7). In a real-world study examining the drug survival of adalimumab, the median time to discontinuation was 36 weeks suggesting that drug survival is reduced in patients with HS and highlighting the continuing need for effective, durable therapies in HS (30). Options for severe, widespread flares of HS include intravenous (IV) ertapenem or oral glucocorticoids. However, both of these rescue therapies obviously cannot be used long-term for disease control due to the risk of antibiotic resistance and glucocorticoid toxicity, respectively.

Surgical intervention has been shown to offer the highest likelihood of disease resolution (31). However, this therapy is not a viable option for patients with multiple affected areas. Even for patients who may be candidates due to having an isolated affected area, this therapy can be disfiguring and requires significant recovery time.

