### **9.2.2.2 Main analytical approach**

The primary endpoint will be analyzed with the primary estimand defined according to the following attributes:

- Endpoint: Percentage of participants achieving HiSCR50 at Week 16.
- Treatment condition: SAR442970 will be compared to placebo.
- Analysis population: Biologic and small molecule immunosuppressive-naïve population.
- Intercurrent events:
  - Starting or increase in dose of oral antibiotic therapy during the Treatment Period: Participant will be considered as non-responder (composite strategy).
  - Starting selected prohibited medications: Participant will be considered as non-responder. Details of selection will be specified in the SAP (composite strategy).
  - Starting other prohibited medications: Data collected after use will be used to determine the responder/non-responder status (treatment policy strategy).
  - Discontinuation of study intervention due to lack of efficacy: Participant will be considered as non-responder (composite strategy).
  - Discontinuation of study intervention (due to reasons other than lack of efficacy): All data collected after treatment discontinuation will be used to determine the responder/non-responder status (treatment policy strategy).
- Population-level summary: The primary efficacy analysis will be the comparison between SAR442970 and placebo in the percentage of participants achieving HiSCR50 at Week 16, using a Bayesian logistic regression model including treatment group and adjusted by randomization stratum (Hurley stage). The statistical analysis will be conducted following a Bayesian approach using an informative prior on the placebo response rate based on the historical studies available.

Missing data will be imputed to non-responders when HiSCR50 is missing.

Data will be presented graphically, where applicable, and with summary statistics by visit and by treatment regimen. Difference of response rate, and the 80% and 90% credibility intervals, will be provided.

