## 9.5 SAMPLE SIZE DETERMINATION

Data from historical studies which have similar target population and study design will be used as prior information supplementing the placebo arm, using a Bayesian approach. A prior distribution of the percentage of participants that achieved HiSCR50 at Week 16 of the placebo arm was determined based on the data observed in the historical studies ([41](#)).

For the biologic and small molecule immunosuppressive-naïve population, an informative prior distribution for the placebo group HiSCR50 rate has been chosen as a beta distribution with parameter (████). This prior distribution contributes an approximate effective sample size of ██████ participants for the placebo treatment group. Sample size calculations were performed to ensure reasonable accuracy for the estimation of the response rate. ██████

Table 10 (42).

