**Table 10 - Accuracy of the 80% credible interval in the biologic and small molecule immunosuppressive-naïve population**

| SAR442970
incidence rate (n) | Placebo rate
(n) | Lower limit | Upper limit | Half-width |
|---------------------------------|---------------------|-------------|-------------|------------|
|                                 |                     |             |             |            |

A sample size of 66 participants randomized in a █ ratio to SAR442970 versus placebo will provide a half-width for the 80% credible interval of less than 0.145 which is deemed sufficient.

For TNF-experienced population, an informative prior distribution for the placebo group HiSCR50 rate has been chosen as a beta distribution with parameter (████). This prior distribution contributes an approximate effective sample size of 2 participants for the placebo treatment group. Sample size calculations were performed to ensure reasonable accuracy for the estimation of the response rate. █████

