$$\ln\left(\frac{E(y)}{1-E(y)}\right) = \text{logit}(E(y)) = \beta_{PBO}X_{PBO} + \beta_{TRT}X_{TRT} + \beta_{HS2}X_{HS2} + \beta_{HS3}X_{HS3}$$

Where X_{PBO}, X_{TRT} are dummy variables taking the value 1 or 0 according to whether or not each of participant is in the placebo or SAR442970 treatment group respectively, X_{HS2}, X_{HS3} are dummy variables taking the value 1 or 0 according to whether or not each of participant is in the Hurley stage II or III groups respectively.

For parameter estimation, the following constraint will be used:

$$\beta_{HS2} = -\beta_{HS3}$$

Giving the model:

$$\ln\left(\frac{E(y)}{1-E(y)}\right) = \text{logit}(E(y)) = \beta_{PBO}X_{PBO} + \beta_{TRT}X_{TRT} + \beta_{HS2}(X_{HS2} - X_{HS3})$$

so that the influence of Baseline Hurley Stage on the model estimated treatment group mean responses are more evident.

The expectations of the prior distributions for the biologic and small molecule immunosuppressive-naïve population in the placebo group response rates will be set to match the observed treatment group response rates in the available historical studies. An informative prior distribution for the HiSCR50 rate has been chosen as a beta distribution with parameter (2.1; 4.9) which have expectations equal to 30% for the placebo group to match the observed treatment group response rates of the historical studies. A vague uninformative prior (a prior with a large variance) will be used for the biologic and small molecule immunosuppressive-naïve population in the treatment group because there are few to no prior data published on SAR442970 in HS).

IF p_{TRT}, p_{PBO} denote the probability of response in the treatment group and placebo group respectively, to map the probability scale priors for the group response rates and the logit scale treatment group we will use the following equations :

$$p_{PBO} = \text{logit}^{-1}(\beta_{PBO})$$

$$p_{TRT} = \text{logit}^{-1}(\beta_{TRT})$$

Accordingly, the priors to be used are :

$$\beta_{PBO} \sim \beta (2.1; 4.9)$$

$$\beta_{TRT} \sim N (0; 10000)$$

$$\beta_{HS2} \sim N (0; 10000)$$

The model equation will be updated to parameterize β_{PBO} as the model intercept with the active treatment being additive effects (on the logit scale). We note that model (2) can be re-parameterized as follows:

$$\beta_{PBO} = \gamma_{PBO}$$

$$\beta_{TRT} = \gamma_{TRT} + \gamma_{PBO}$$

$$\beta_{HS2} = \gamma_{HS2}$$

Giving the model:

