2.2.3 Frequentist analysis

Frequentist analysis (non-Bayesian) of the primary endpoint will be implemented to provide complementary perspective, offering validation and robustness checks to the Bayesian results. Furthermore, by incorporating informative priors in Bayesian analysis, the subsequent use of frequentist analysis allows for the examination of how these prior assumptions influence the final results, enhancing transparency and understanding.

Treatment difference in achieving HiSCR50 (SAR442970 versus placebo), and the treatment response rates in each intervention group will be provided using the CMH method stratified by baseline Hurley stage. Handling of IEs will follow that of the primary approach. Missing data will be imputed as non-responders. The reported results will include 80% and 90% confidence intervals of the treatment difference.

2.2.4 [REDACTED]

[REDACTED]

[REDACTED]

[REDACTED]

[REDACTED]

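### SAP 2.2.2 lists the Beta(2.1; 4.9) placebo prior on the logit coefficient, while its own text puts that prior on the HiSCR50 rate

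*SAP*

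**What the plan says.** The primary analysis is a Bayesian logistic regression of Week 16 HiSCR50 in the naïve population. It has a coefficient for each arm and one for Hurley stage. SAP 2.2.2 makes three statements about the placebo prior.

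1. In prose, the informative "prior distribution for the HiSCR50 rate has been chosen as a beta distribution with parameter (2.1; 4.9) which have expectations equal to 30" per cent in the placebo group.
2. It says that, "to map the probability scale priors for the group response rates and the logit scale treatment group we will use the following equations", and sets p_PBO equal to the inverse logit of beta_PBO. This makes beta_PBO a log-odds.
3. The list of priors that closes the derivation prints "\beta_{PBO} \sim \beta (2.1; 4.9"). Next to it stand normal priors with parameters (0; 10000) for beta_TRT and beta_HS2.

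The re-parameterised model then sets beta_PBO = gamma_PBO, so the listed prior becomes the prior of the intercept.

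The protocol agrees with the prose. Section 9.2.2.2 describes an analysis "using an informative prior on the placebo response rate based on the historical studies available", and section 9.5 says that "an informative prior distribution for the placebo group HiSCR50 rate has been chosen as a beta distribution with parameter" values that are redacted there. SAP section 3 repeats the statement in 9.5.

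**The concern.** Statements 1 and 2 together put the Beta distribution on the rate. Statement 3 puts it on the logit of the rate. These are different priors, and only the first has the stated 30% mean.

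The list is the part that gets turned into code. Its other two entries are correctly on the logit scale, so nothing in it signals that the first entry needs a transformation. Every primary result depends on this prior: the posterior response rates, the 80% and 90% credible intervals, and the posterior probability that the difference exceeds zero. Under the printed line the placebo posterior can never fall below 50%, whatever the data show, so an effective drug could be reported as having no effect or a harmful one.

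**Working it through.** **Inputs.** Beta(2.1; 4.9), the inverse-logit link and the vague normal priors come from SAP 2.2.2. The naïve target of 66 and the 2:1 ratio come from SAP 1.1 and give 44 active and 22 placebo. Observed rates are assumed, because the planning rates are redacted. Expected responder counts may be fractional (30% of 22 = 6.6).

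**The plan's own figure.** On the rate scale the prior mean is 2.1/(2.1 + 4.9) = 2.1/7.0 = 0.30, as stated. The effective size is 7, the 80% prior interval is 10.2% to 52.7%, and 87% of the mass lies below 50%.

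**The printed line.** If beta_PBO ~ Beta(2.1; 4.9), then beta_PBO lies in (0, 1).
- Lower limit of the placebo rate: 1/(1 + e^0) = 50.0%.
- Upper limit: 1/(1 + e^-1) = 73.1%.
- Prior mean, by integrating the inverse logit over the Beta density: 57.4%. The 80% prior interval is 52.6% to 62.9%.
- A 30% rate needs beta_PBO = ln(0.3/0.7) = -0.85, which is outside the support.

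These limits depend on no sample size or data.

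**Effect on the posterior, without the Hurley term.** With 6.6/22 placebo responders, the rate-scale posterior is Beta(2.1 + 6.6; 4.9 + 15.4) = Beta(8.7; 20.3), with mean 8.7/29.0 = 30.0%. As printed, the posterior is proportional to the Beta density in beta_PBO times the binomial likelihood on (0, 1), and the mean placebo rate is 54.6%. The active arm is the same in both (flat on the logit), so the shift is 30.0 - 54.6 = -24.6 points at every active rate.

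| Placebo v active | Difference, rate scale | Difference, as printed |
|---|---|---|
| 30% v 40% | 10.0 | -14.6 |
| 30% v 50% | 20.0, P(diff>0) 0.96 | -4.6, P 0.28 |
| 30% v 60% | 30.0, P 0.995 | 5.4, P 0.755 |
| 30% v 70% | 40.0 | 15.4 |
| 30% v 80% | 50.0 | 25.4 |
| 26% v 42% | 15.0, P 0.91 | -12.4, P 0.06 |
| 28% v 59% | 30.5, P 0.996 | 4.5, P 0.72 |

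The last two rows use the adalimumab results cited in protocol 2.1.1, of which the first reads "42% of treated patients achieved HiSCR50 versus 26% of placebo-treated patients at Week 12". They are illustrations only: this trial's endpoint is at Week 16 and has its own non-response rules.

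The shift varies with the observed placebo count: about -33 points at 4/22, -23 at 7/22 and -11 at 11/22.

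**Full model with the Hurley term.** This takes equal Hurley strata and reads 10000 as a variance. For 7/22 v 24/44, the rate-scale prior gives 23.5 points (80% interval 8.8 to 37.8, P = 0.98). The printed prior gives -0.2 points (-10.6 to 10.1, P = 0.50). Leaving out the Hurley term does not drive the result.

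**Side evidence on intent.** Protocol 9.5 says that the naïve sample "will provide a half-width for the 80% credible interval of less than 0.145 which is deemed sufficient". At 30% placebo and 30-80% active, the rate-scale half-width is 0.132-0.144, just inside that limit. The printed prior gives 0.084-0.103.

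**The case against.** The strongest reply is that the intent is clear and this is a notation slip. The prose, the 30% mean, the mapping equations, SAP section 3 and the protocol all put the prior on the rate, and one line departs from them. That stands, and it is why the correction is simple. It does not make the printed line harmless, because a SAP should not rely on its reader to override the list of priors.

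Second, the harm requires literal coding, which would be conspicuous. The posterior placebo rate, about 54.6%, would be reported beside a raw rate of 30%. SAP 2.2.3 also adds a CMH analysis, described as "offering validation and robustness checks to the Bayesian results". This is fair: the by-arm descriptive statistics, the posterior summaries and the CMH results could all expose the error. They would do so only once unblinded results exist, and none of them corrects the pre-specified prior.

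Third, the half-width evidence is weak. The protocol states only an upper bound, which the printed prior also meets, and the rate-scale match depends on the assumed 30%: at 32% v 50% the half-width is 0.1453. This is correct. The figure is consistent with the rate scale but does not prove it, and the conclusion does not rest on it.

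Fourth, a symbol may have been lost when the formula was read from the PDF. This cannot be wholly excluded, but the neighbouring formulas carry their inverse logit intact. A look at the typeset SAP page settles it.

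**Conclusion.** The concern holds. SAP 2.2.2 specifies two incompatible placebo priors for the primary analysis, and the one in its list of priors is wrong by the SAP's own account, since it cannot produce the stated 30% mean. That conclusion, and the 50% floor on the placebo rate, follow from the link function alone.

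The size is conditional on the line being coded as printed. With 44 v 22 participants and an observed placebo rate near 30%, the estimated difference falls by about 25 points. True-looking differences of up to roughly 24 points would then appear as null or negative. The shift is smaller if the placebo rate is higher and larger if it is lower. The documents do not show the program, so whether the error would reach the results is unknown. Because the primary result depends on this line, it should be corrected rather than left to interpretation.

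**What to change.** In the list of priors in SAP 2.2.2, replace the first line with p_PBO ~ Beta(2.1; 4.9), and add that beta_PBO = gamma_PBO = logit(p_PBO). Leave the vague normal priors on beta_TRT and beta_HS2. It is worth adding that the prior on gamma_TRT = beta_TRT - gamma_PBO then follows and is not specified separately.

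Check that the analysis program implements the rate-scale prior. A simple test is to run it without data and confirm a prior mean placebo rate of 30%, not 57.4%. Do this before the treatment codes are released for the primary analysis. If they have already been released, record which prior the program used.

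The cost is one line of SAP text and a code check, with no new data and no effect on trial conduct.

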2.2.3 Frequentist analysis

Frequentist analysis (non-Bayesian) of the primary endpoint will be implemented to provide complementary perspective, offering validation and robustness checks to the Bayesian results. Furthermore, by incorporating informative priors in Bayesian analysis, the subsequent use of frequentist analysis allows for the examination of how these prior assumptions influence the final results, enhancing transparency and understanding.

Treatment difference in achieving HiSCR50 (SAR442970 versus placebo), and the treatment response rates in each intervention group will be provided using the CMH method stratified by baseline Hurley stage. Handling of IEs will follow that of the primary approach. Missing data will be imputed as non-responders. The reported results will include 80% and 90% confidence intervals of the treatment difference.

2.2.4 [REDACTED]

[REDACTED]

[REDACTED]

[REDACTED]

[REDACTED]

2.3 SECONDARY EFFICACY ENDPOINT(S) ANALYSIS

The endpoints detailed in this section are the secondary efficacy endpoints. Other secondary endpoints analyses are defined in [Section 2.7.2](#) (AE, SAE), [Section 2.7.3.1](#) (laboratory abnormalities) and [Section 2.8](#) (Others analyses).

2.3.1 Time to onset of achieving HiSCR50

The time to onset of achieving HiSCR50 by Week 16 will be defined as [date of first time achieving HiSCR50 - date of randomization] in days.

The estimand for time to event endpoint defined in [Table 3](#) will be used. The following IEs will be handled with the composite variable strategy; participants will be censored at Week 16:

- Starting or increase in dose of oral antibiotic therapy prior to Week 16
- Starting selected prohibited medications prior to Week 16. Participants that receive the selected treatment [Table 5](#) will be reviewed in a blinded fashion to make sure the medication was used due for HS treatment failure and not an unrelated condition
- Discontinuation of study intervention due to lack of efficacy

The following IEs will be handled with the treatment policy strategy (without IEs that need to be handled with composite variable strategy). Data collected after starting such IE will be included.

- Starting other prohibited medications
- Discontinuation of study intervention due to reasons other than lack of efficacy

Participants discontinuing the study follow-up before Week 16 will be censored at the time of their last HS clinical parameters assessment.

Comparison of treatment response (SAR442970 vs Placebo) will be summarized using the Cox proportional hazards model, including intervention groups, and stratified by baseline Hurley Stage. The hazards ratios and the 80% and 90% confidence intervals. Kaplan-Meier curves along with associated summary statistics will be provided by intervention group.

2.3.2 Absolute change from Baseline in IHS4 at Week 16

The IHS4 is a validated tool to assess HS severity. The determination of IHS4 requires counting inflammatory nodules, abscesses and draining tunnels and multiplying each by a specific coefficient making it straightforward to apply in both research and clinical practice and easy to use in conjunction with the HiSCR50. A continuous IHS4 score can be derived based on this weighted score. A categorial IHS4 score can also be derived from the weighted score: a total score of 3 or less signifies mild, 4 to 10 signifies moderate, and 11 or higher signifies severe disease.

Two IHS4 scores are to be derived from the primary continuous IHS4. The first one is defined as the improvement by at least one IHS4 stage at Week 16 and the second which is also known as IHS4-55 is defined as a 55% reduction in IHS4 score from Baseline.

The change from baseline in the IHS4 score at Week 16 will be analyzed using the ANCOVA model including the baseline value, intervention group and baseline Hurley Stage.

The estimand for continuous endpoints defined in [Table 3](#) will be used. The IE handling is as follow:

- Data of participants starting or increasing the dose of oral antibiotic therapy for HS during the treatment period or started selected prohibited medication listed in [Table 5](#) or discontinued study intervention because of lack of efficacy will be excluded after such IE, and participant's worst postbaseline value on or before the time of the IE will be used to assign the endpoint value (WOCF). Participants with no post-baseline value, the baseline value will be used. Participants that receive the selected treatment listed in [Table 5](#) will be reviewed in a blinded fashion to make sure the medication was used due for HS treatment failure and not an unrelated condition.
- For participants who started other prohibited medication or discontinue the treatment prematurely due to other reasons than efficacy, all data collected after the event will be used in the analysis.

Missing data at Week 16 will be imputed with participant worst postbaseline value. For participants with no post-baseline value, the baseline value will be used.

The least square (LS) means of the absolute change from baseline to Week 16 in IHS4 per study invention group will be reported. The difference of SAR442970 against placebo in LS means and the corresponding 80% and 90% confidence intervals will be reported. Descriptive statistics will also be provided.

2.3.3 HS Skin Pain NRS at Week 16

The HS-Skin Pain NRS is a unidimensional numeric rating scale (NRS) that allows for rapid measure of skin pain that can be administered multiple times with minimal administrative burden. The HS-Skin Pain NRS is scored on a 0 to 10 scale with 0 indicating “no skin pain” and 10 indicating “worst skin pain possible”. The HS-Skin Pain NRS has a 24-hour recall period and will be completed as a daily diary, ideally at the same time each day (evening) throughout the Treatment Period.

The percentage of participants achieving at least 30% reduction and at least 1 unit reduction from Baseline in weekly average of daily HS Skin Pain NRS at Week 16 among participants with Baseline NRS ≥ 3 (HS-Skin Pain NRS is based on worst skin pain in a 24-hour recall period [daily assessment is averaged over 7-day period]) will be analyzed. Participants must have a minimum of 4 diary entries within the 7-day period prior to Week 16 to calculate the week's average. Those who don't meet this requirement will have missing data for that week.

The estimand for skin pain endpoint will be used and participants with missing data will be imputed as non-responders. The following IEs will be handled with the composite variable strategy; participants will be considered as non-responders after such IE.

- Using analgesic therapy within 5 days of Week 16 will be considered as non-responders.
- Starting selected prohibited medications. Participants that receive the selected treatment listed in Table 5 will be reviewed in a blinded fashion to make sure the medication was used due for HS treatment failure and not an unrelated condition.
- Discontinuation of study intervention due to lack of efficacy.

The following IE will be handled with the treatment policy strategy (without IEs that need to be handled with composite variable strategy). Data collected after starting such IE will be included.

- Discontinuation of study intervention due to reasons other than lack of efficacy.

Participants with missing data will be imputed as non-responders.

An estimate of the treatment difference (SAR442970 versus placebo) will be obtained using CMH method, stratified by baseline Hurley stage. The estimated treatment difference will be reported along with the 80% and 90% confidence intervals.

